2.4.5.2 Deaths

The following summaries of deaths will be generated for the safety population.

- Number (%) of patients who died during the study
- Treatment-emergent adverse events leading to death (death as an outcome on the adverse event case report form page as reported by the Investigator) by primary SOC and PT.

Listing will be provided for all deaths with flags indicating TEAE period or post-treatment period status.

2.4.5.3 Analyses of laboratory variables

Hematology, blood chemistry and urinalysis are performed in local laboratories in this study.

The summary statistics (including number, mean, median, SD, minimum and maximum) of all laboratory variables (laboratory values and changes from baseline) will be calculated for each visit or study assessment (baseline, each post baseline time point, endpoint) by treatment group. This section will be organized by biological function as specified in [Section 2.1.4.3](#).

The incidence of PCSAs (list provided in [Appendix A](#)) at any time during the treatment-emergent adverse event period will be summarized by biological function and treatment group whatever the baseline level and/or according to the following baseline status categories:

- Normal/missing
- Abnormal according to PCSA criterion or criteria

The incidence of abnormal laboratory values at any time during the TEAE period will be summarized in shift tables by biological function and treatment group whatever the baseline level and/or according to the following baseline status categories:

- Normal/Missing
- Abnormal high according to the normal range
- Abnormal low according to the normal range

For parameters for which no PCSA criteria are defined, similar table(s) using the normal range will be provided.

For bacterial infection testing, results will be summarized as number of patients (counts and percent) with negative and positive levels by treatment group.

2.4.5.4 Analyses of vital sign variables

The summary statistics (including number, mean, median, standard deviation, minimum and maximum) of all vital sign variables (vital signs values and changes from baseline) will be calculated for each visit or study assessment (daily from baseline to Day 29) by treatment group.

The incidence of PCSAs at any time during the treatment-emergent adverse event period will be summarized by treatment group irrespective of the baseline level and/or according to the following baseline status categories:

- Normal/missing
- Abnormal according to PCSA criterion or criteria

Listings will be provided for patients with at least one post-baseline PCSA values.

2.4.5.5 Analyses of physical examination

Physical examination data which is only collected at screening will not be summarized.

2.4.5.6 Analyses of electrocardiogram variables

Listing of patient ECG variables at screening will be provided.

2.4.5.7 Analyses of anti-sarilumab antibodies

The following summary will be provided separately for ADA positive patient, ADA negative patient.

ADA prevalence and titer

The following summary will be provided based on the ADA population:

- Number (%) of patients with an ADA positive sample at baseline
 - The summary statistics (including number, median, Q1, Q3, minimum and maximum) of the titer for the baseline ADA positive patients
- Number (%) of patients with an ADA negative sample at baseline

ADA incidence and titer

The following summary will be provided based on the ADA population during TEAE period:

- Number (%) of ADA-negative patients
- Number (%) of ADA-positive patients
 - The summary statistics (including number, median, Q1, Q3, minimum, and maximum) of the peak post-baseline titer for all ADA-positive patients
- Number (%) of treatment-emergent ADA-positive patients.

- The summary statistics (including number, median, Q1, Q3, minimum, and maximum) of the peak post-baseline titer for treatment-emergent ADA-positive patients
- Number (%) of treatment-boosted ADA positive patients.
- The summary statistics (including number, median, Q1, Q3, minimum, and maximum) of the peak post-baseline titer for all treatment-boosted ADA-positive patients

In addition, number (%) of patients with ADA positive or negative response at each visit will be summarized by treatment group.

Plot of percentage of patients with treatment-emergent ADA positive response at each visit will be provided by treatment group.

Listing for ADA status will also be provided.

ADA and PK

Descriptive summary of sarilumab concentrations in serum will be provided by ADA patient classifications (positive or negative) over time for the sarilumab treatment group by number of sarilumab doses.

ADA and clinical efficacy

The primary and key secondary efficacy endpoints will be analyzed by ADA patient classifications (positive or negative).

ADA and clinical safety

The safety assessment will focus on the following events:

- Hypersensitivity (standardized MedDRA query (SMQ): Hypersensitivity [Narrow])
- Anaphylaxis (SMQ: Anaphylaxis [Narrow])
- IV infusion reaction (HLT: IV infusion reaction)
- TEAEs leading to permanent treatment discontinuations

Number (%) of patients with these events will be summarized by ADA patient classifications (positive or negative) for the sarilumab treatment group.

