PK/Biomarkers (Central Laboratories):											
Serum for PK/Sarilumab Concentration 		X 	X 	X 	X	X	X	X 			X 
ADA		X				X 		X			X
Serum IL-6 		X		X	X	X	X	X			X
Serum sIL-6R 		X 						X			X
Blood for PCR SARS-CoV-2  (Not for determining the inclusion criteria)		X		X	X	X	X	X			X
Pharmacogenomics (optional genomic study):											
Blood for DNA/RNA 		X									

ESO: end of study, SpO2: oxygen saturation, CT-scan: computed tomography ECG: electrocardiogram, WOCBP: women of childbearing potential, PK: pharmacokinetic, ADA: antidrug antibodies, sIL-6R: soluble interleukin 6 receptor, IL: interleukin, PCR: polymerase chain reaction, SARS-CoV-2: Severe acute respiratory syndrome coronavirus 2, DNA: deoxyribonucleic acid, RNA: ribonucleic acid, SAE: serious adverse event, AESI: adverse event of special interest.

1. Laboratory-confirmed SARS-CoV-2 infection (eg by PCR), or other commercial or public health assay in any specimen within 2 weeks prior to randomization and no alternative explanation for current clinical condition is required for inclusion.
2. Screening and baseline may occur within 24 hours. Assessments that are noted for both visits should only be assessed once if the baseline visit is within 24 hours of the screening visit. All baseline samples, if obtained, should be collected before study drug administration at baseline visit except post-infusion PK and sIL-6R samples.
3. Patients will have an end of study (EOS) assessment to collect data on survival, adverse events, and history of hospital re-admission. This assessment may be performed by phone. This visit may be performed earlier if a patient withdraws from the study.
4. Patients discharged prior to Day 29 will have a follow-up phone call on Day 29 to collect data on all adverse events, and history of hospital re-admission.
5. Patients discharged prior to Day 29 should have a sample collected on or before day of discharge. Any sample collected within 24 hours of the day of discharge do not need to be repeated.

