22. Sarilumab concentration
  - Day 1 sampling: 2 samples with one taken pre dose, and 1 taken within 30 min after the end of infusion; end of infusion sample should be collected from the arm contralateral to that used for IV infusion

- For patients administered a 2nd dose, Day 2 or Day 3 sampling is performed with 2 samples taken on the day of the 2nd dose, with 1 taken pre dose, and 1 taken within 30 min after the end of infusion; end of infusion sample should be collected from the arm contralateral to that used for IV infusion
- Day 4 (approximately 72 hours post first dose)
- The Day 29 or Early Discharge PK sample may be used for ADA analysis

23. In the event of any SAE of severe infusion reaction, or any AESI of anaphylactic reaction or systemic allergic reaction that is related to IMP, ADA samples will be collected at or near the onset of the event for any additional analysis.

24. Serum IL-6 samples must be taken pre-dose. Samples are mandatory for baseline/Day 1, Discharge before Day 29 and Day 29. It is optional on Day 4, 7, 15, and 21.

25. Serum sIL-6R:

- Day 1 sample taken pre dose (as close to initiation of treatment as reasonable)

26. Blood collected will be shipped for the central analysis of SARS-CoV-2 viral load and is not for determining the inclusion criteria.

27. Separate consent is required for participation in the optional genomic sub-study and collection of a blood sample for (DNA/RNA). The sample for genomic DNA/RNA should be collected on Day 1 or may be collected at any visit.

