2.1.4.7 Anti-sarilumab antibodies

Samples analyzed in the antidrug antibody (ADA) assay will be categorized as either positive or negative.

ADA positive patient is defined as patient with at least 1 treatment-emergent or treatment-boosted ADA positive sample during the TEAE period, where

- Treatment-emergent ADA positive patient is defined as a patient with non-positive assay (meaning negative or missing) response at baseline but with a positive assay response during the TEAE period.
- Treatment-boosted ADA positive patient is defined as a patient with a positive ADA assay response at baseline and with at least a 4-fold increase in titer compared to baseline during the TEAE period.

ADA negative patient is defined as patient without a treatment-emergent or treatment-boosted ADA positive sample during the TEAE period.

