2.3.4 ADA population

The ADA population includes all patients who had at least 1 post-baseline valid ADA sample following the first dose of study drug.

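### Efficacy by post-baseline ADA class, timed from first dose with no landmark, can show an ADA association when none exists

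*SAP*

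**What the plan says.** SAP 2.4.5.7, under the ADA and clinical efficacy item, gives one sentence: "The primary and key secondary efficacy endpoints will be analyzed by ADA patient classifications (positive or negative". It does not name the analysis population, the arms, a landmark or a time-dependent method. In the same section, the prevalence and incidence summaries are tied to the ADA population, and the PK and safety items are limited to sarilumab-treated patients. The efficacy item has neither limit.

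Two definitions bear on who is classified:

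- SAP 2.3.4: "The ADA population includes all patients who had at least 1 post-baseline valid ADA sample following the first dose of study drug". A post-dose sample is required.
- SAP 2.1.4.7: "ADA positive patient is defined as patient with at least 1 treatment-emergent or treatment-boosted ADA positive sample during the TEAE period", and "ADA negative patient is defined as patient without a treatment-emergent or treatment-boosted ADA positive sample during the TEAE period". The negative class requires no sample.

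The sampling rules are in Protocol 1.3. The ADA row has entries at baseline, Day 15 (marked with footnote 23), Day 29 and discharge before Day 29, and none on Days 2 to 7. Footnote 5 says "Patients discharged prior to Day 29 should have a sample collected on or before day of discharge". Footnote 22 adds "The Day 29 or Early Discharge PK sample may be used for ADA analysis". Footnote 23 concerns severe infusion reactions and IMP-related anaphylactic or systemic allergic events, for which "ADA samples will be collected at or near the onset of the event for any additional analysis".

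SAP 2.4.4 counts time to event from first dose. SAP 2.4.4.1 counts live discharge as a primary event. The key secondary endpoint is being alive at Day 29.

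**The concern.** ADA class is known only after dosing, and the time at which it is read depends on the outcome.

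- **Survival.** A patient who dies in hospital before Day 15 normally has no post-dose ADA sample. To be found ADA-positive, a patient must first survive to a sample.
- **Time to improvement.** A patient discharged early has one early chance to test positive, at about the time of the primary event. A patient at score 4 needs score 6 or 7, so the event falls at or near discharge. A patient at score 2 or 3 can meet the endpoint in hospital before any sample is due. Slow improvers are tested later. Patients need not return after discharge, so later positivity will normally go unseen.

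Comparing efficacy across such a class from first dose mixes any real ADA effect with the effect of having lived, or stayed in hospital, long enough to be sampled. What is at stake is an immunogenicity table that could be read as ADA changing survival or recovery.

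**Working it through.** **The plan's own figure.** The documents give no figure for the ADA analysis. The only design figure is at least 90% power for 160 versus 80 patients (SAP 1.3). With exponential hazards, 45% and 70% improved at Day 15 give HR = ln(0.30)/ln(0.55) = 2.01. Events by Day 15 are 80×0.45 + 160×0.70 = 148. The Schoenfeld formula gives power = Φ(ln 2.01 × √(148×1/3×2/3) − 1.96) = 98.0%. With 199 events by Day 29 it is 99.7%. The stated bound holds, and the ADA question does not touch it.

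**Null check.** Suppose ADA has no effect on any outcome. Assumptions not in the documents:

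- Day 29 mortality of 5, 10 or 20%
- 55% discharged by Day 15 (set within the plan's 45 to 70% improvement range)
- 15% eventually ADA-positive, with onset at minimum 5 and mean 12 days, or minimum 10 and mean 20 days
- constant competing hazards of discharge and in-hospital death, no missed samples and no event-driven samples

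Solving for the daily hazards (discharge, death) gives 0.0552 and 0.0036; 0.0574 and 0.0077; 0.0636 and 0.0180.

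*Step 1: share of Day 29 deaths with no post-dose sample, if Day 15 sampling is routine.* With λ the sum of the two hazards, the share is (1 − e^(−15λ))/(1 − e^(−29λ)). At 10% mortality λ = 0.0651 and the share is 0.623/0.849 = 73%. At 5% and 20% it is 72% and 78%.

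*Step 2: survival inside the ADA population.* At 10% mortality: 0.90/(0.90 + 0.10×0.265) = 97.1%. At 5% and 20% it is 98.5% and 94.8%, against true values of 95% and 80%.

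*Step 3: ADA-positive minus ADA-negative survival.* Simulation used 2 million patients per scenario; ranges cover the two onset assumptions.

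| Day 29 mortality | ADA population only (SAP 2.3.4) | Unsampled counted as negative (SAP 2.1.4.7) |
|---|---|---|
| 5% | −0.2 to −0.7 points | +3.1 to +3.5 points |
| 10% | −0.7 to −1.6 points | +6.1 to +6.7 points |
| 20% | −2.7 to −4.0 points | +11.8 to +12.6 points |

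Hand check at 10% mortality with earlier onset: 7.06% of patients are found positive, and 95.67% of them survive. If unsampled patients count as negative, survival in the negative class is (0.90 − 0.0706×0.9567)/(1 − 0.0706) = 89.6%, a difference of +6.1 points. In the ADA population (92.64% of patients) it is (0.90 − 0.0706×0.9567)/(0.9264 − 0.0706) = 97.3%, a difference of −1.6 points.

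*Step 4: discharge by Day 15.* The simulation gives 8 to 32% in ADA-positive patients. In ADA-negative patients it gives 60 to 68% (ADA population) or 56 to 57% (unsampled counted as negative). The mechanism is the reading time. With the earlier onset, the chance of being found positive at a Day 7 discharge is 0.15×(1 − e^(−2/7)) = 3.7%. At a Day 29 sample it is 0.15×(1 − e^(−24/7)) = 14.5%.

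*Step 5: if the Day 15 entry, which carries footnote 23, means event-driven sampling only.* No in-hospital death by Day 29 then has a scheduled post-dose sample. In the ADA population, survival is 100% in both classes. With unsampled patients counted as negative, it is 100% in positives against about 95%, 89 to 90% and 79% in negatives.

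**The case against.** The best case for leaving the text alone has three parts.

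1. The analysis is peripheral. It is outside the four-step hierarchy in SAP 2.4.4.3, has no specified ADA test or interaction, and sits in the immunogenicity section. Protocol 9.4.5.3 plans only ADA listings and counts. This stands, and it limits the importance of the point.

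2. A reader might infer that ADA status exists only for patients who reach a late or discharge sample, so that survival is near 100% by construction and early deaths contribute nothing. The documents do not support that. SAP 2.1.4.7, taken literally, makes an unsampled early death ADA-negative. Footnote 23 allows earlier event-driven samples. If Day 15 sampling is routine, later deaths are captured, and survival in the ADA population is inflated but not fixed at 100%. This part stands against the stronger reading only: both ways of handling unsampled patients distort the comparison, in opposite directions for survival.

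3. A reader might also infer that slow improvers will be ADA-positive because antibodies take time to form. That depends on ADA onset and incidence, which the documents do not give. This stands as a limit on size. It does not remove the dependence of sampling time on outcome, which follows from the schedule.

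**Conclusion.** The point holds. ADA class is set after dosing and partly by the outcome it is meant to explain, and nothing in the SAP corrects for this. With no true ADA effect, a spurious association can appear whichever definition governs unsampled patients. The SAP leaves that choice open, and with it the direction of the survival bias.

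Under the assumptions above and routine Day 15 sampling, the survival artefact runs from a 4.0-point deficit to a 12.6-point advantage for ADA-positive patients, and the artefact in discharge by Day 15 is larger. These sizes are illustrative, since mortality, discharge rate, ADA incidence and onset are all assumed. A reader should not infer that the trial's main conclusions are at risk: the hierarchical tests do not use ADA class. This is a cheap improvement.

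**What to change.** - Drop Day 29 survival by ADA class measured from first dose.
- For the primary endpoint, restrict to the sarilumab arms and do one of two things. Either use a landmark at the Day 15 sample, among patients alive, hospitalized and event-free then, with ADA status known by then and time counted from the landmark. Or give only a descriptive listing with the limitation stated. The landmark sample must be named, because patients sampled at discharge have already had the event and are no longer at risk.
- Reconcile SAP 2.1.4.7 with SAP 2.3.4, so that it is clear whether a patient with no post-dose sample is ADA-negative or unclassified.
- State whether the Day 15 ADA sample is routine or only event-driven. If it is only event-driven, the landmark is not available and the listing remains.

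The cost is a few sentences, fewer patients and a less standard immunogenicity table. At the plan's own 70% improvement by Day 15, at most 0.30×160 = 48 patients per planned sarilumab arm would be event-free at the landmark, fewer after deaths. At an assumed 15% positivity that is about 7 ADA-positive patients (0.15×48), so the listing may be the practical choice. The SAP's list of protocol amendments stops at Amendment 03. If it is revised for the closure of the 200 mg arm, this change can go in at the same time.

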2.4.6 Analysis of pharmacokinetics

Analysis of drug concentration data:

The concentrations of sarilumab over time and pharmacokinetic parameters, as appropriate, will be summarized using descriptive statistics by treatment group and number of sarilumab doses using the PK population.

No formal statistical hypothesis testing will be performed.

2.4.7 Analysis of Pharmacodynamic and Exploratory Biomarker Data:

The concentrations of CRP, IL-6, and sIL-6R over time will be summarized using descriptive statistics by treatment group using the safety population. The analysis will include:

- Observed value, change from baseline and percent change from baseline by each sampling point through Day 29 /EoS.
- The figures of mean \pm standard error (SE) versus scheduled sampling time points.

In addition, ANC will be analyzed similarly.

As an exploratory analysis, the percentage of patients with SARS-CoV-2 positive (either nasopharyngeal swab or PCR) over time will be summarized using the safety population.

The relationship between d-dimer, ferritin, LDH, IL-6, neutrophil:lymphocyte ratio and the clinical assessment using the 7-point ordinal scale will be explored.

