### 1.3 SCHEDULE OF ACTIVITIES (SOA)

Study Procedure	Screening Visit 	Baseline Visit 	Follow-up Until Hospital Discharge							EO S 	Discharge Before Day 29 
			2 or 3	4	7	15	21	29 	60		
Day	-1 or 1	1									
Window (day)										±7	
Screening/Baseline:											
Inclusion/Exclusion For a positive SARS-CoV-2 test qualification, see footnote 		X									
Informed Consent	X										
Pharmagenomics Sub-Study Consent	X										
Demographics and Medical History	X										
History of hypercapnic respiratory failure 	X										
Randomization		X									
Treatment:											
Study Drug Administration			X	X 							
Assessments:											
Efficacy											
Body Temperature 	X (4 times a day)		Day 1-3: 4 times a day, Day 4-29: 2 times a day							X	
Oxygen Delivery and Oxygenation 	X (4 times a day)		Day 1-3: 4 times a day Day 4-29: record results as assessed							X	
Resting SpO2 	X (4 times a day)		Day 1-3: 4 times a day Day 4-29: record results as assessed							X	
Clinical Daily Assessment (including 7-point ordinal scale) 	X		Daily until discharge							X	
Vital Status (and cause of death)			Daily until discharge						X	X	
Arterial blood gas results (as available) 			X								
Vital Signs  (other than temperature and SpO2)	X		Daily until discharge							X	
Targeted physical examination	X										

Study Procedure	Screening Visit 	Baseline Visit 	Follow-up Until Hospital Discharge							EO S 	Discharge Before Day 29 
			2 or 3	4	7	15	21	29 			
Day	-1 or 1	1							60		
Window (day)									±7		
Optional Electrocardiogram (ECG) 	X										
Record Concomitant Therapy 	X										X
Adverse Events 	X									X	X
Pregnancy Test (WOCBP) 	X										
Bacterial infection testing and fungal infection testing (blood)					X	X					
Laboratory Testing Standard-of-Care (Local Laboratories):											
Hematology Results 	X	X 	X 	X	X	X	X	X			X
Blood Chemistry Results 	X	X 	X 	X	X	X	X	X			X
Urinalysis 	X					X					
Urine Culture Results (if available) 	X					X					
Optional nasopharyngeal swab for SARS-CoV-2 detection 		X			X	X	X	X			X

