6. Patients may receive a second dose with study drug 24 to 48 hours after the first dose, if the patient meets prespecified criteria in [Section 4.1](#). Day 2 or 3 samples are only taken from patients who are administered a second dose of study treatment. They should be drawn prior to administration of the second dose of study drug to aid in benefit/risk assessment.
7. Sites are required to capture the history of chronic hypercapnic respiratory failure.
8. Body temperature is described in [Section 8.1.2](#) (up to 4 times a day at screening). Retrospective temperature within the previous 24 hours can be considered for screening. Body temperature to be reported in the CRF should be the maximum value observed during any time period or window ([Section 8.1.2](#)).
9. Oxygen delivery and oxygenation: refer to [Section 8.1.2](#) of the protocol for details (up to 4 times a day at screening). Retrospective readings within the previous 24 hours can be considered for screening.
10. Must be measured after 5 minutes of rest (sitting or supine), and must be measured simultaneously with oxygen delivery and ventilation data.
11. Clinical Data Assessments (including 7-point ordinal scale, status of intubation, Intensive care unit admission/discharge, CT scan, X-rays, and any other imaging performed during hospitalization, daily consciousness for NEWS2 scoring system [2]): refer to [Section 8.1.1](#) of the protocol for details.
12. Results as reported to be recorded in arterial blood gas results electronic case report form (CRF) (as available).
13. Vital signs include height (screening only), weight (screening only), blood pressure, pulse, and respiration rate, See [Section 8.2.1](#)
14. The ECG is optional. Historical ECG from current hospital admission is acceptable.
15. Concomitant therapy: refer to [Section 6.5](#) of the protocol for details.
16. Adverse events: All AEs will be recorded in CRF. Note: any abnormal physical findings requiring medical or surgical intervention must be recorded as an AE.
17. Pregnancy testing to be performed locally in women of childbearing potential (WOCBP) only. Serum or urine pregnancy test are both acceptable.
18. Hematology: refer to [Table 11](#) for details.
19. Blood Chemistry: refer to [Table 11](#) for details.
20. Urinalysis is performed at screening (if feasible) and should be collected one additional time (optional) during the treatment period.
21. SARS-CoV-2 detection will be performed locally. This test is optional.

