### **Tertiary/exploratory**

- Evaluate the virologic changes in the treatment arms compared to the control arm as assessed by:
  - Percent of patients with SARS-CoV-2 detectable in nasopharyngeal (NP) sample at days 7, 15, 21, and 29
  - Quantitative SARS-CoV-2 virus in the NP sample at days 7, 15, 21, and 29
  - Development of SARS-CoV-2 variants in NP sample at day 7, 15, 21, and 29
  - Quantitative SARS-CoV-2 virus in blood at days 7, 15, 21, and 29
- To evaluate the cytokine profile and additional biomarkers that may be associated with efficacy and safety associated with sarilumab treatment
- To evaluate the incidence of new or worsening laboratory-confirmed serious secondary infections in the treatment arms as compared to the control arm
- To characterize the concentrations of sarilumab in serum over time
- Patients will not be recalled after discharge for any missing exploratory assessments.

---

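### The SAP's only virologic summary mixes optional swabs with scheduled blood PCR, and leaves at least three of the protocol's four virologic endpoints without a planned analysis

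*SAP*

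**What the plan says.** Protocol Table 2 lists four virologic endpoints under the tertiary/exploratory heading, each tied to a specimen and to Days 7, 15, 21 and 29:

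- "Percent of patients with SARS-CoV-2 detectable in nasopharyngeal (NP) sample at days 7, 15, 21, and 29"
- the amount of virus in the NP sample
- development of viral variants in the NP sample
- "Quantitative SARS-CoV-2 virus in blood at days 7, 15, 21, and 29"

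The objective above them is a comparison of the treatment arms with control. Protocol section 9.4.4 leaves the analysis of exploratory endpoints to the SAP.

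The two specimens are collected on different terms. The Schedule of Activities row for the swab reads "Optional nasopharyngeal swab for SARS-CoV-2 detection", and footnote 21 says "SARS-CoV-2 detection will be performed locally. This test is optional". The row "Blood for PCR SARS-CoV-2" carries no optional mark, and footnote 26 says "Blood collected will be shipped for the central analysis of SARS-CoV-2 viral load".

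SAP section 2.1.6 names both specimens and refers to the protocol for timing, without deriving any variable. SAP section 2.4.7 then gives the single analysis: "the percentage of patients with SARS-CoV-2 positive (either nasopharyngeal swab or PCR) over time will be summarized using the safety population". It names no days. It also does not mention treatment group, although the same section does so for CRP, IL-6 and sIL-6R.

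**The concern.** The chance of being positive on at least one of two specimens rises with the number of specimens tested. If one specimen is optional, a percentage positive on either reflects how many patients were swabbed as well as how many carry detectable virus. Its level, its course over time and any contrast between arms then become hard to interpret.

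The summary also does not match what the protocol set out to measure. Blood is sent to a central laboratory for viral load, but no quantitative summary of it is planned. At stake is whether the trial can report its stated virologic comparison in a readable form.

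**Working it through.** The plan gives no figure to reproduce here, so the check sets the texts side by side and then illustrates the size.

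**1. Endpoints against planned analyses**

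| Protocol Table 2 endpoint | SAP 2.4.7 read as one pooled percentage | SAP 2.4.7 read as two separate percentages |
|---|---|---|
| Percent NP-detectable | not computed | covered |
| Quantitative NP virus | none | none |
| NP variants | none | none |
| Quantitative blood virus | none | none |

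Coverage is 0 of 4 on the pooled reading and at most 1 of 4 on the other.

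**2. Specimens by day in the Schedule of Activities**

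| | Baseline | Day 4 | Days 7, 15, 21, 29 | Discharge |
|---|---|---|---|---|
| NP swab (optional, local) | yes | no | yes | yes |
| Blood PCR (scheduled, central) | yes | yes | yes | yes |

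Even with full compliance, the specimen mix changes between Day 4 and Day 7. One caveat is that protocol section 4.1 and SAP section 1.1 give a different list for both specimens (Days 1, 4, 7, 15 and 29). The Day 4 point therefore rests on the Schedule, to which SAP section 2.1.6 defers by citing the protocol schedule.

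**3. The missing counting rule**

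SAP section 2.5.3 leaves patients with missing data out of percentages unless otherwise specified. It does not say whether a patient with one specimen of two counts as missing. Two rules are possible:

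- Rule A keeps every patient with any result.
- Rule B keeps only patients with both results, so the denominator is the swabbed group and Day 4 has none under the Schedule.

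**4. Illustration**

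All inputs are assumed, because the documents give none. Let b be blood positivity, q NP positivity if swabbed and s the share swabbed. Everyone has a blood result, the two tests are independent, and swabbing is unrelated to the result.

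- Rule A: percent positive = 1 − (1 − b)(1 − s·q)
- Rule B: percent positive = 1 − (1 − b)(1 − q)

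With b = 15% and q = 50%, Rule A gives:

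- none swabbed: 1 − 0.85 × 1.00 = 15.0%
- half swabbed: 1 − 0.85 × 0.75 = 36.3%
- all swabbed: 1 − 0.85 × 0.50 = 57.5%

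With half swabbed, Rule B gives 57.5% where Rule A gives 36.3%, so the unstated rule alone moves the result by about 21 points.

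Under Rule A, moving s from 0 to 100% shifts the percentage by (1 − b)·q. For b of 5 to 30% and q of 30 to 70%:

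- smallest: 0.70 × 0.30 = 21.0 points
- largest: 0.95 × 0.70 = 66.5 points

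For two arms with identical virology, 40% swabbed in one and 60% in the other, the gap is 0.20 × (1 − b)·q:

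- smallest: 0.20 × 0.70 × 0.30 = 4.2 points
- largest: 0.20 × 0.95 × 0.70 = 13.3 points

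If instead every blood-positive patient is also NP-positive, with NP 60% and blood 15%, the gap is 0.20 × (0.60 − 0.15) = 9.0 points, which lies inside that range.

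**The case against.** The strongest reply is that pooling is inferred. The SAP gives no derivation, section 2.1.6 lists the two measurements separately, and PCR names a method without naming a specimen. That it means the blood sample is deduced from section 2.1.6 and the Schedule row. One percentage per specimen is a possible reading, though a less natural one. This stands as a caveat: a reader might infer that none of the protocol's virologic endpoints is computed, but that holds only on the pooled reading. Three endpoints are unplanned on either reading.

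Other inferences also go further than the documents allow:

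- **That an unswabbed, blood-negative patient is planned to count as negative.** No such rule is written. The defect is that no rule is given.
- **That swab uptake will differ by arm.** Nothing shows this. The trial is double-blind with one common schedule, and the swab is listed at discharge for all patients. A 20-point gap is an assumption.
- **That blood data will be near complete.** Protocol section 4.1 says samples will be requested and SAP section 1.1 says they may be obtained. Sampling stops at discharge.
- **That viral clearance is a designated safety question.** The protocol places virology under exploratory objectives. It is not among the safety endpoints, adverse events of special interest or stopping criteria.
- **That reporting by specimen removes all bias.** It removes the specimen-mix artefact. Selection into optional swabbing remains.

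Finally, the analysis is descriptive and exploratory, so the consequence is small. That is correct.

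**Conclusion.** The concern holds in limited form. As written, the summary depends on specimen mix, lacks a rule for patients with one specimen, and does not match the specimen-specific endpoints in protocol Table 2. Quantitative blood virus, quantitative NP virus and NP variants have no planned analysis, although the protocol leaves their specification to the SAP. Percent NP-detectable is covered only if two separate percentages were meant.

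The text establishes these gaps but not their numerical effect. The range of about 4 to 13 points depends on the assumed positivity rates, the assumed 40% versus 60% uptake, independence of the two tests, and a denominator of all patients with any result. There is no effect on alpha, power, or the primary and key secondary endpoints. This is a minor point, worth correcting because the correction is cheap.

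**What to change.** Replace the sentence in SAP section 2.4.7 with the following:

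- Report NP and blood results separately, by treatment group, at Days 7, 15, 21 and 29. Give percent detectable among patients with a valid sample of that type, and the number sampled per arm.
- Summarise blood viral load as log10 value and change from baseline, with a stated convention for results below the detection limit.
- Add the quantitative NP and variant analyses, or state that they are dropped because the optional local swab may not support them. Footnote 21 speaks only of detection.
- State that NP results remain subject to selection, because swabbing is optional and discharged patients are not recalled for exploratory assessments. The number sampled per arm shows this but does not correct it.

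If the either-specimen percentage is kept beside these tables, give its counting rule.

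The cost is a short SAP edit and a few tables. The percent-detectable and blood viral load summaries use samples already planned. The documents do not show whether quantitative NP or variant data will exist, so that item may reduce to a statement that the endpoints are dropped.
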